4.7.1.3 Reporting of serious adverse events

Investigators and other centre personnel must inform appropriate AstraZeneca representatives via the web based data capture (WBDC) system of any SAE that occurs in the course of the study within 1 calendar day (i.e., immediately but no later than the end of the next business day) of when he or she becomes aware of it. Follow-up information on SAEs must also be reported by the Investigator within the same time frame.

The AstraZeneca representative will work with the investigator to compile all the necessary information and ensure that all the necessary information is provided to Bristol-Myers Squibb Global Pharmacovigilance and Epidemiology within one calendar day of initial receipt for fatal and life threatening events and within three calendar days of initial receipt for all other SAEs.

All SAEs have to be reported, whether or not considered causally related to the investigational product or to the study procedure(s). SAE information will be entered and submitted into the WBDC system on the relevant eCRF modules. If the system is unavailable, the Investigator should fax a paper back-up SAE report to the AstraZeneca representative immediately, recognising that the same reporting time frames still apply. The Investigator is responsible for completing the eCRF as soon as the system becomes available again. The AstraZeneca representative will forward all information relevant to the SAE to Bristol-Myers Squibb Pharmacovigilance via fax or email.

AstraZeneca or the Investigator is responsible for informing the Ethics Committees of the SAE as per local requirements. Reporting of SAEs to Regulatory Authorities is the responsibility of Bristol-Myers Squibb.

4.7.2 Laboratory safety measurements and variables

4.7.2.1 Methods of assessment

Blood and urine specimens will be collected for laboratory analyses. The date and time of sampling will be recorded on the laboratory requisition form. The samples will be processed by a central laboratory and results will be reported back to the clinic within 72 hours.

Due to the fasting laboratory assessments, all patients will visit the clinic on a fasting stomach in the morning, before 11 a.m..The patients will be instructed not to have ingested any food or beverages 12 hours before visiting the clinic (however, drinking water is allowed). Also, the patients will be instructed not to take the investigational product, insulin or other OADs in the morning before visiting the clinic. Allowed concomitant medication can be taken with water only.

All samples should be taken by adequately trained study personnel and handled in accordance with given instructions in the laboratory manual. Up to date reference ranges will be provided during the study and laboratory results will be compared to the laboratory standard normal ranges and flagged if they are outside the normal range. The Investigator should make an assessment of the available results with regard to clinically significant abnormalities. The laboratory reports should be signed and dated and retained at centre as source data for laboratory variables.

For information on how AEs based on laboratory tests should be recorded and reported, see section [4.7.1.2](#)

The complete list of safety laboratory tests is displayed in [Table 6](#) below. The laboratory tests are conducted following the assessment schedule outlined in section [4.7.2.1](#). In case a patient experiences sustained elevated liver safety abnormalities additional blood sampling needs to be performed. For further guidance please refer to CSP [Appendix H](#) - Algorithm on Management of Sustained Elevated Liver Safety Abnormalities.

Table 6 Safety laboratory variables for Enrolment, 24-Week Double-Blind Treatment Period and 80-Week long term Double-Blind Extension Period I and II

Visit	1	2	3	4	5	6	7	8	9	10	11	12	13	14	15	16	17	18	19	
Study Week	-2	0	1	4	8	12	16	20	24	32	40	48	49	52	65	78	91	104	107	
Haema-tology																				
Haemo-globin	X	X	X	X	X	X	X	X	X	X	X	X		X	X	X	X	X	X	
Haematocrit	X	X	X	X	X	X	X	X	X	X	X	X		X	X	X	X	X	X	
Red blood cell count	X	X	X	X	X	X	X	X	X	X	X	X		X	X	X	X	X	X	
Erythrocyte mean corpuscle volume	X	X	X	X	X	X	X	X	X	X	X	X		X	X	X	X	X	X	
Erythrocyte mean corpuscle haemoglobin concentration	X	X	X	X	X	X	X	X	X	X	X	X		X	X	X	X	X	X	
Reticulo-cytes	X	X	X	X	X	X	X	X	X	X	X	X		X	X	X	X	X	X	
White blood cell count and differential	X	X	X	X	X	X	X	X	X	X	X	X		X	X	X	X	X	X	
Platelet count	X	X	X	X	X	X	X	X	X	X	X	X		X	X	X	X	X	X	
Clinical chemistry (serum)																				
Aspartate Aminotransferase (AST, SGOT)	X	X	X	X	X	X	X	X	X	X	X	X		X	X	X	X	X	X	
Alanine Aminotransferase (ALT, SGPT)	X	X	X	X	X	X	X	X	X	X	X	X		X	X	X	X	X	X	
Alkaline Phosphatase (AP)	X	X	X	X	X	X	X	X	X	X	X	X		X	X	X	X	X	X	
Creatine Kinase (CK)	X	X	X	X	X	X	X	X	X	X	X	X		X	X	X	X	X	X	
Total Bilirubin (TB)	X	X	X	X	X	X	X	X	X	X	X	X		X	X	X	X	X	X	
Blood Urea Nitrogen (BUN)	X	X	X	X	X	X	X	X	X	X	X	X		X	X	X	X	X	X	
Electrolytes ^g	X	X	X	X	X	X	X	X	X	X	X	X		X	X	X	X	X	X	
Total protein	X	X	X	X	X	X	X	X	X	X	X	X		X	X	X	X	X	X	
Albumin	X	X	X	X	X	X	X	X	X	X	X	X		X	X	X	X	X	X	

Visit	1	2	3	4	5	6	7	8	9	10	11	12	13	14	15	16	17	18	19
Study Week	-2	0	1	4	8	12	16	20	24	32	40	48	49	52	65	78	91	104	107
Uric acid	x	x	x	x	x	x	x	x	x	x	x	x		x	x	x	x	x	x
Serum Creatinine (SCr), calculated creatinine clearance (Cockcroft-Gault formula) ^a	x	x	x	x	x	x	x	x	x	x	x	x		x	x	x	x	x	x
Serum Cystatin C			x							x		x				x		x	x
Serum Bone Metabolism Marker (Parathyroid Hormone (PTH) and 25-hydroxy vitamin D)			x							x		x				x		x	x
Follicle Stimulating Hormone (FSH)	x																		
TSH ^e	x																		
Hepatitis Screen Panel ^f	x																		
Urinalysis																			
Glucose ^b	x	x	x	x	x	x	x	x	x	x	x	x		x	x	x	x	x	x
Blood by dipstick ^c	x	x	x	x	x	x	x	x	x	x	x	x		x	x	x	x	x	x
Albumin	x	x	x	x	x	x	x	x	x	x	x	x		x	x	x	x	x	x
Total protein	x	x	x	x	x	x	x	x	x	x	x	x		x	x	x	x	x	x
Creatinine	x	x	x	x	x	x	x	x	x	x	x	x		x	x	x	x	x	x
Calculated Urinary albumine: creatinine ratio (UACR)	x	x	x	x	x	x	x	x	x	x	x	x		x	x	x	x	x	x
Calculated total protein : creatinine ratio	x	x	x	x	x	x	x	x	x	x	x	x		x	x	x	x	x	x
Pregnancy test ^d	x	x	x	x	x	x	x	x	x	x	x	x		x	x	x	x	x	x

a Creatinine clearance will be calculated by the method of Cockcroft and Gault.

b Results will be blinded.

c Microscopy if dipstick positive for blood.

d Urine or serum pregnancy test (see section 4.7.1.2)

Revised Clinical Study Protocol
Drug Substance Dapagliflozin
Study Code **D1690C00006**
Edition Number 5
Date

- e If abnormal, measure free T4.
- f Includes Hepatitis B viral antibody IgM, Hepatitis B surface antigen and Hepatitis C virus antibody
- g Sodium, Bicarbonate, Potassium, Chloride, Calcium, Magnesium, Phosphorus
- h Total Bilirubin (mg/dL, mmol/L) Reflex testing of Direct (Conjugated) and Indirect (Unconjugated) Bilirubin if TB > 1.5X ULN.

4.7.2.2 Derivation or calculation of outcome variables

Creatinine clearance will be calculated by the method of Cockcroft and Gault.

4.7.3 Vital signs, ECG and physical examination

Vital signs (pulse and BP), ECG, weight, height and physical examination results will be obtained. For the timing of individual measurements, see [Table 1](#) and [Table 2](#)

4.7.3.1 Methods of assessment

Pulse and blood pressure

Pulse measurement will be taken after the patient has been sitting and resting for at least 5 minutes and before blood samples are taken. The pulse measurement will be followed by 3 BP measurements obtained at least 1 min apart on the reference arm, using a standardized cuff adapted to the size of the patient's arm. All 3 readings have to be recorded. For analysis the average of the 3 BP readings will be used. BP readings will be taken with the patients comfortably in a seated position with the arms raised to the level of the heart and in a supported position. All readings should be recorded as accurately as possible and the same BP measurement device should be used for all assessments for a given patient. The reference arm, is defined as the arm with has been used for systolic BP measurements at the baseline visit. The reference arm should be used for all BP measurements through the entire study

Orthostatic blood pressure

At selected visits where orthostatic BP is measured, measurements should be obtained following completion of seated blood pressure.

The supine BP must be measured prior to the standing BP. The patient should rest in the supine position for at least 5 minutes prior to measurement of BP. Supine BP will be determined from three replicate measurements obtained at least 1 minute apart. All 3 readings have to be recorded. For analysis the average of the 3 BP readings will be used.

The patient will then stand for 2 to 3 minutes. After this time, measure the BP with the arm supported at the antecubital fossa at heart level. Standing BP will be determined from three replicate measurements obtained at least 1 minute apart. All 3 readings have to be recorded. For analysis the average of the 3 BP readings will be used. All readings should be recorded as accurately as possible and the same BP machine should be used for all assessments for a given patient.

ECG

A 12-lead ECG will be taken (supine position, standard ECG with a recommended paper speed of 50 mm/second covering at least 6 sequential beats) after the patient has been lying down resting for at least 5 minutes. The ECG will be evaluated by the investigator and entered as 'Normal' or 'Abnormal' in the eCRF. If the ECG is evaluated as "Abnormal" the investigator has to further specify the abnormality that was detected.

One original ECG print-out, signed and dated by the investigator, will be kept in the medical records, ensuring a copy is maintained in the source documents for the study.

Weight and height

The patient's weight will be recorded in kilogram (kg), to one decimal place, on a fasting stomach with light clothing and no shoes. The patient's height will be recorded in centimetres, with no shoes. All readings should be recorded as accurately as possible and the same scale should be used for all assessments for a given patient.

Waist circumference

The waist should be measured in the standing position at the natural waist (smallest waist circumference). If there is no natural waist, the measurement should be made at the level of the umbilicus. Measurements should be made at the end of normal inspiration with a centrally measuring tape supplied by AZ.

Physical examinations

- A brief physical examination should include cardiovascular, lungs, abdomen, and extremities; and any organ systems pertinent to the patient's signs, symptoms, or adverse events. Presence of oedema should always be checked.
- A complete physical examination should include general appearance, head, eyes, ears, nose, throat, neck, cardiovascular, lungs, abdomen, lymph nodes, extremities, neurological, skin, and musculoskeletal. Presence of oedema should always be checked.

Baseline data is collected at visit 2, and new findings at the following physical examinations are recorded as change from baseline.

4.7.3.2 Derivation or calculation of outcome variables

BMI will be computed by AstraZeneca.

$BMI = \text{weight} / \text{height}^2$ (where weight is measured in kg, and height in metres).

The mean BP measurements (of 3 measurements) will be computed by AstraZeneca for each patient at each visit.

4.7.4 Other safety measurements and variables - SMBG and UTI / GI

Values from self-monitoring of fasting plasma glucose will be monitored daily through the entire study. SMBG values and data regarding hypoglycaemic events as well as daily insulin use will be collected in a patient diary.

4.7.4.1 Methods of assessment

Self-monitoring of fasting plasma glucose should be done in order to reduce risk of prolonged periods of undetected hyperglycaemia or to confirm hypoglycaemia. Patients will be asked to do self-monitoring of fasting plasma glucose using glucometers provided by AstraZeneca. The patients will receive instructions how to use the glucometer, according to the manufacturer's instruction.

The memory of the glucometer should be reviewed to compare with the patient's diary, as applicable. The glucose values should be reviewed by the site to identify any unusual high or low values, to confirm that the values (from the glucometer's memory and/or from the patient's diary) were obtained for the patient and to calculate the mean insulin dose. If finger stick glucose values are discordant from glycaemic control assessed by the central laboratory or with clinical symptoms, the patient's glucometer should be tested and the procedure for using it reviewed with the patient.

Fasting plasma glucose concentrations

Fasting plasma glucose should be self-monitored. The glucometer will be calibrated to show plasma glucose levels. The patient diary will be reviewed and collected from visit 1 on and kept in the investigator study file. A new diary for the next period will be dispensed to patients continuing in the study.

If at least 3 fasting SMBG diary measurements from the past 7 days exceed

240 mg/dl (13,3 mmol/l) at V3, V4, V5, V6

220 mg/dl (12.2 mmol/l) at V7, V8, V9

180mg/dl (9.9 mmol/l) at V10, V11, V12

the investigator should consider up-titration of insulin. In this case the corresponding SMBG values should be recorded in the eCRF.

Up-titration of the insulin dose during the long-term, double-blind extension period II should be considered by the investigator if HbA1c measured by central laboratory is

- >7.5 % at V14, V15,
- >7.0 % at V16, V17, V18

Insulin dose should not be uptitrated if both the following scenarios are met:

1. A patient has experienced unexpected hypoglycemic event/s

and

2. An uptitration of insulin may put the patient at an increased risk of hypoglycaemia in the clinical opinion of the investigator.

An unexpected hypoglycemic event is an hypoglycemic event that cannot be explained by circumstances such as missing a meal, or extensive physical exertion.

If a patient experiences an unexpected hypoglycemic event in spite of high FPG or HbA1c levels, the investigator should consider a change in timing of the insulin dose and/or a change of the insulin regimen, rather than considering uptitration of the insulin dose.

The last HbA1c and FPG values measured by central laboratory prior to the increase in insulin dose will be carried forward for the efficacy analyses at week 24 (visit 9).

Reduction of daily insulin dose will not be allowed except for reasons of patient safety under the following circumstances:

Reduction of insulin dose shall be ordered by the investigator if the patient reports two of more readings of plasma glucose value ≤ 70 mg/dl (≤ 3.8 mmol/l). In addition, the investigator may consider an insulin dose adjustment (dose reduction or change in timing of insulin dose) in patients who report symptoms suggestive of hypoglycaemia without confirmatory glucose measurements if, in the opinion of the investigator, the patient is at increased risk of further hypoglycemic episodes without such insulin dose adjustments.

Diary fasting SMBG values that meet these criteria should be recorded in the eCRF.

Hypoglycaemic events

The patient will be asked to always self-monitor fasting plasma glucose in case of symptoms suggestive of hypoglycaemia and to register any signs of hypoglycaemia in the supplied diary.

- A hypoglycaemic event can be either
- An episode with symptoms and confirmed low glucose.
- An episode with low glucose.
- An episode with symptoms suggestive of hypoglycaemia when glucose was not measured.

For the evaluation of hypoglycaemic events special attention will be given to hypoglycaemia as defined in accordance with CPMP guidance on clinical investigation of medicinal products in the treatment of diabetes mellitus, as described below.

- Major hypoglycaemic events, defined as symptomatic events requiring external assistance due to severe impairment in consciousness or behaviour, with a capillary or plasma glucose value < 54 mg/dL (< 3.0 mmol/L), and prompt recovery after glucose or glucagon administration.

- Minor hypoglycaemic event, defined as either a symptomatic event with a capillary or plasma glucose value <63 mg/dL (<3.5 mmol/L), and no need for external assistance, or an asymptomatic blood glucose measurement <63 mg/dL (<3.5 mmol/L).
- Events suggestive for hypoglycaemia, with symptoms that the patient experiences as hypoglycaemia and no confirmative measurement.

Data to be collected for each hypoglycaemic event:

- Date of start and stop and time of the day for start
- If symptoms are present or not and which symptoms
- If fingerstick value obtained and the plasma glucose value
- Intervention needed for recovery and possible contributing factors
- Time of last drug administration
- Time of last meal

The patient diary will be reviewed and data regarding hypoglycaemic events transcribed into the eCRFs at each clinical visit. A new diary for the next period will be handed over to the patient if needed. If a major hypoglycaemic event occurs, or more than one minor event since last visit, the patient should contact the investigator. For recording of hypoglycaemic events/symptoms suggestive of hypoglycaemic events as AEs, see section [4.7.1.1](#) and [4.7.1.2](#).

Reduction of insulin dose shall be ordered by the investigator under the following circumstances:

Within the first 7 days of active randomized treatment:

- if the patient report two or more readings of plasma glucose value ≤ 80 mg/dl (≤ 4.4 mmol/l).

After the first 7 days of active randomized treatment:

- if the patient report two or more readings of plasma glucose value ≤ 70 mg/dl (≤ 3.8 mmol/l).

Patients should be encouraged to contact the investigator in such a case to allow the reduction of insulin dose.

Background OAD therapy may only be decreased if a concern of hypoglycaemia arises in a patient that has already been completely taken off of insulin. If background OAD therapy needs to be reduced, the last HbA1c and FPG values measured prior to the reduction in other OAD dose will be carried forward for the efficacy analyses at week 24.

Background OAD therapy may not be increased at any time during the study

Urinary and Genital Infections

The following is presented to assist in the classification and management of infections of the urinary and genital tracts. It is not intended to supplant investigators' clinical judgement:

Asymptomatic bacteriuria is defined as the presence of $\geq 10^5$ colony forming units/mL of bacteria, in a properly collected voided urine specimen, without signs or symptoms typically attributed to urinary tract infection. Asymptomatic bacteriuria is prevalent among diabetic women, and is associated with pyuria in 70% of cases. Neither the Infectious Diseases Society of America nor the U.S. Preventive Services Task Force recommends screening for, or treatment of, asymptomatic bacteriuria in non-pregnant diabetic patients ([Nicolle LE et al 2005](#), [US Preventive Services Task Force 2004](#)). In this study, the central laboratory will not routinely report the results of urinary dipstick tests for leukocyte esterase as a screening test for pyuria in surveillance urine examinations.

At every scheduled visit starting from the randomization visit, the investigator will question subjects about symptoms of urinary tract infections, including but not limited to pain or burning or uncomfortable pressure in the lower abdomen/pelvic area while passing urine, blood in the urine, and symptoms of urinary urgency (a strong and uncontrolled urge to pass urine). If based on the response to these questions or other suggestive signs or symptoms (dysuria, urgency or frequency of urination, suprapubic or perineal discomfort, flank, back, or abdominal pain, costovertebral angle tenderness, nausea, vomiting, fever, chills, or sepsis) the investigator believes that a urinary tract infection may be present, urine cultures (in a local laboratory) should be obtained to confirm a presumptive diagnosis of cystitis, urinary tract infection, pyelonephritis, or prostatitis. Mid-stream clean catch urine collections are recommended. Clinical judgment and local standards of care should apply to decisions concerning therapy.

Study drug should be held in subjects with clinical evidence of upper tract UTI (e.g. pyelonephritis) or presumed urosepsis until the course of treatment of the infection has been completed and clinical recovery has occurred. It is recommended that a follow-up urine culture is obtained within 7 days of clinical recovery from a documented urinary tract infection. Whether additional therapy is prescribed because of culture results should be determined by Investigator judgment, after consultation with the Study Team Physician.

In addition, at every scheduled study visit starting from the randomization visit, the investigator will question subjects about symptoms of genital infections including but not limited to itching, soreness or redness in the genital area and a change or increase in genital discharge. The diagnosis of vaginitis, vulvovaginitis, vulvitis or balanitis can be made based on physical examinations, culture of secretions or a therapeutic response to treatment of fungal or other vaginal pathogens. A urine culture is not required for diagnosis of genital infections if the diagnosis is confirmed by physical examination, culture of secretions, or a therapeutic response to treatment of fungal or other vaginal pathogens.

Also, it is the investigator's responsibility to report, as applicable based on investigator's judgment and subject's medical history, related adverse events as defined in Section 4.7.1. Additional information, including but not limited to completion of supplemental eCRFs may be requested for certain adverse events and/or laboratory abnormalities which are reported/identified during the course of the study.

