- if at least 3 fasting SMBG diary measurements from the past 7 days exceed 220 mg/dl (12.2 mmol/l). Diary fasting SMBG values that meet these criteria should be recorded in the eCRF.

The last HbA1c and FPG values measured by central laboratory prior to the up-titration of insulin dose will be carried forward for the efficacy analyses at week 24 (visit 9).

Reduction of daily insulin dose shall be ordered by the investigator under the following circumstances:

Within the first 7 days of active randomized treatment:

- if the patient reports two or more readings of plasma glucose value ≤ 80 mg/dl (≤ 4.4 mmol/l).

After the first 7 days of active randomized treatment:

- if the patient reports two or more readings of plasma glucose value ≤ 70 mg/dl (≤ 3.8 mmol/l).

Patients should be encouraged to contact the investigator in such a case to allow the reduction of insulin dose.

Background OAD therapy may only be decreased if a concern of hypoglycaemia arises in a patient that has already been completely taken off of insulin.

Background OAD therapy may not be increased at any time during the study

Patients will be discontinued from the study if they have had complete withdrawal of both insulin and if applicable other OAD, they subsequently experience more than one event of major hypoglycaemia, and the investigator decides that current treatment puts the patient at risk of either repeated hypoglycaemic events or major hypoglycaemia. Major hypoglycaemia is defined as a symptomatic event requiring external assistance due to severe impairment in consciousness or behaviour with a capillary or plasma glucose value < 3 mmol/l (< 54 mg/dl) and prompt recovery after glucose or glucagon administration.

Randomized patients who discontinue early should complete the procedures described for visit 18 (end of treatment period) immediately following discontinuation of study drug. Thereafter patients should return for the 3 week follow up visit so that visit 19 procedures can be completed.

Long-term, double-blind extension period I (Visits 10–12, Weeks 25-48)

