6.2 Description of outcome variables in relation to objectives and hypotheses

The primary objective of the study is to assess the efficacy of 2.5 mg, 5 mg and 10 mg dapagliflozin compared to placebo as add-on therapy to insulin in improving glycaemic control in subjects with type 2 diabetes who have inadequate glycaemic control on ≥ 30 IU injectable insulin daily for at least 8 weeks prior to enrolment, as determined by the change in HbA1c levels from baseline to week 24. The objective will be statistically analyzed using Dunnett's method (overall type I error rate for the primary endpoint 0.05). The significance level for each pair-wise group comparison of dapagliflozin versus placebo will be approximately 0.019.

Key secondary objectives are to compare the effects of each dose of dapagliflozin versus placebo given as add-on therapy to insulin after a 24-week double-blind treatment period by evaluation of:

1. The change in body weight from baseline to week 24
2. The absolute change in calculated mean daily insulin dose from baseline to week 24
3. The proportion of subjects with calculated mean daily insulin dose reduction from baseline to week 24

4. The change in FPG from baseline to week 24

The statistical testing of the primary and key secondary outcome variables will proceed in a sequential manner, to control the type I error rate within each dapagliflozin group at the 0.05 level. Specifically, the significance or non-significance of the treatment comparisons for the primary outcome variable will determine which, if any, statistical inferences are made for the key secondary outcome variables. Only those dapagliflozin groups significantly superior to placebo for the primary outcome variable will have statistical inference versus placebo for the first key secondary outcome variable, (1). Then, the testing for the other key secondary outcome variables will proceed so that

- the significance or non-significance of the treatment comparisons for (1) will determine which, if any, statistical inferences are made in treatment comparisons for (2), and
- the significance or non-significance of the treatment comparisons for (2) will determine which, if any, statistical inferences are made in treatment comparisons for (3), and
- the significance or non-significance of the treatment comparisons for (3) will determine which, if any, statistical inferences are made in treatment comparisons for (4).

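### Section 4.7.4.1 contradicts Section 3.1, and itself, on when insulin is to be reduced in the first 7 days, and leaves symptom-only reductions before week 24 unclear

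*Protocol*

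**What the plan says.** Section 3.1, in the part on the 24-week double-blind period, opens its rule with "Reduction of daily insulin dose shall be ordered by the investigator under the following circumstances". For the first 7 days the trigger is "if the patient reports two or more readings of plasma glucose value ≤ 80 mg/dl (≤ 4.4 mmol/l"; after that it is "if the patient reports two or more readings of plasma glucose value ≤ 70 mg/dl (≤ 3.8 mmol/l". No reduction on symptoms alone is listed for this period. In the parts on extension periods I and II, Section 3.1 keeps the 70 mg/dl trigger and adds a discretionary adjustment for patients with symptoms but no glucose value.

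Section 4.7.4.1 states the reduction rule twice.

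- Under the sub-heading on fasting plasma glucose it says "Reduction of daily insulin dose will not be allowed except for reasons of patient safety under the following circumstances". The circumstances that follow are a mandatory reduction "if the patient reports two of more readings of plasma glucose value ≤ 70 mg/dl (≤ 3.8 mmol/l", and an adjustment that the investigator may consider "in patients who report symptoms suggestive of hypoglycaemia without confirmatory glucose measurements". No study period is given.
- Under the sub-heading on hypoglycaemic events it returns to the two-stage rule: for the first 7 days, "if the patient report two or more readings of plasma glucose value ≤ 80 mg/dl (≤ 4.4 mmol/l", and 70 mg/dl afterwards. The symptom-only option is absent.

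Section 6.2 lists the absolute change in calculated mean daily insulin dose as key secondary variable 2. Variable 3 is "The proportion of subjects with calculated mean daily insulin dose reduction from baseline to week 24". Section 6.4.1 analyses insulin-dose endpoints by carrying the last value forward and, unlike the other endpoints, does not cut them off when insulin is titrated.

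**The concern.** One block of Section 4.7.4.1 is worded as a prohibition with exceptions, and its exceptions omit a circumstance in which Section 3.1 and the other block of 4.7.4.1 require a reduction. A site cannot obey both in week 1. The same block opens a discretionary route to reduction that Section 3.1 reserves, by where it places it, for the extensions.

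Two things are at stake. First, this is a hypoglycaemia-safety instruction, and it should read the same wherever a site looks it up. Second, patients are otherwise told to hold their insulin dose constant, so these rules are a main route by which doses fall during the confirmatory period. The resulting doses enter two endpoints in the testing hierarchy. Endpoint 2 gates endpoint 3, and endpoint 3 gates fasting plasma glucose. With about 150 centres and 4 to 5 patients expected at each, there is ample room for practice to differ between sites.

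**Working it through.** No figure in the protocol is in dispute, so the check is a comparison of the texts.

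**Step 1. The five statements side by side.**

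| Place | Period named | Force | Glucose trigger (two or more readings) | Symptom-only option |
|---|---|---|---|---|
| 3.1, 24-week period | First 7 days; then after | Must be ordered | ≤80 mg/dl; then ≤70 mg/dl | Not listed |
| 3.1, extension I | Extension I | Must be ordered, plus discretion | ≤70 mg/dl | Yes |
| 3.1, extension II | Extension II | Must be ordered, plus discretion | ≤70 mg/dl | Yes |
| 4.7.4.1, fasting plasma glucose | None | Not allowed outside the list | ≤70 mg/dl | Yes |
| 4.7.4.1, hypoglycaemic events | First 7 days; then after | Must be ordered | ≤80 mg/dl; then ≤70 mg/dl | Not listed |

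**Step 2. First 7 days.** Take a patient with no symptoms and two readings, both above 70 and up to 80 mg/dl. Rows 1 and 5 require a reduction. Row 4, read as written, does not allow one: the glucose exception is not met and the symptom exception does not apply. The instructions are opposite. Row 5 is in the same section as row 4, so 4.7.4.1 disagrees with itself as well as with 3.1.

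**Step 3. After day 7, up to week 24.** Every row that can apply uses 70 mg/dl, so the glucose trigger does not conflict. The direct contradiction is confined to week 1 and to readings above 70 and up to 80 mg/dl.

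**Step 4. Symptom-only reductions before week 24.** Row 4 permits them with no period limit. Rows 1 and 5 do not mention them, and Section 3.1 gives them only in rows 2 and 3. Row 1 lists when a reduction must be ordered; it does not say that these are the only circumstances. This is permission against silence: an ambiguity, not a second contradiction.

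**Step 5. Does row 4 apply to the 24-week period?** Nothing in it excludes that period. The sentence just before it concerns the week 24 analysis at Visit 9. The same sub-section sets up-titration thresholds from Visit 3 onward, and Section 4.7.4 describes glucose monitoring through the entire study. On the other side, its reduction wording matches rows 2 and 3. Its intended scope cannot be settled from the text.

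**Step 6. Route to the endpoints.** Baseline is the 7-day mean dose at Visit 2. A reduction counts in endpoints 2 and 3 if it is still reflected in the week 24 value, or in the last value carried forward, because these endpoints are not cut off at titration. A week 1 reduction that is later reversed drops out.

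**Step 7. Size.** The protocol gives no expected rate of reductions in any arm and no share of reductions made on symptoms alone. The effect on endpoints 2 and 3 cannot be computed.

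**The case against.** The strongest reply is that a careful site would find a usable rule. Section 3.4.3 sends the reader to Section 3.1 for further information on insulin treatment, and 3.1 sets the rules out by period. The block in 4.7.4.1 looks like extension wording inserted without its period label: its text on unexpected hypoglycaemic events and its reduction wording both appear in 3.1 only for the extensions. The contradiction is also narrow, covering one week and a 10 mg/dl band (80 − 70).

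Much of this stands. The origin is probably editorial, and the pointer softens the problem. It does not remove it: the pointer gives 3.1 no precedence, and the block carries a prohibition without saying where it applies.

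A reader might infer more than the documents support:

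- **That symptom-only reductions are flatly forbidden before week 24 by Section 3.1.** They are not; 3.1 is silent for that period.
- **That the conflict biases the comparison, for instance because discretionary reductions follow a guess at the treatment arm.** All arms are double-blind under the same text, and nothing in the protocol shows a directional effect. More reductions on active drug could be a real drug effect, which these endpoints are meant to capture.
- **That the harm can be expressed as a share of a detectable difference in endpoint 3.** Any such figure rests entirely on assumed reduction rates.
- **That reductions made without a qualifying reading should be set aside in an extra analysis.** This needs a replacement dose that is not defined, and it could remove true effect.

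**Conclusion.** The point holds as an internal inconsistency in the text, not as a criticism of a design choice. Section 4.7.4.1 and Section 3.1 give opposite instructions for a symptom-free patient with two readings above 70 and up to 80 mg/dl in the first 7 days, and 4.7.4.1 gives both instructions. Separately, the protocol does not make clear whether symptom-only reductions are permitted before week 24.

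The consequence is inconsistent practice on a safety instruction, and added inconsistency in the doses that enter key secondary endpoints 2 and 3. This rests on one assumption: that at least some sites follow the block without a period limit as written. No directional bias is shown, and the size is unknown. The reduction rule does not alter the definition or the analysis of the primary HbA1c endpoint. No view is taken here on which clinical rule is right.

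**What to change.** Bring the reduction text of Section 3.1 (24-week period, extension I, extension II) and both blocks of Section 4.7.4.1 into one statement by period: first 7 days, day 8 to week 24, extension I and extension II. Use identical wording in both sections, or state it once in 3.1 and refer to it from 4.7.4.1. The statement must give the study period to which the block under the fasting-glucose sub-heading applies, and must say whether symptom-only reductions apply before week 24. The sponsor decides which rule stands.

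The cost is amendment wording and notice to sites; no change to sample size, endpoints or analysis is needed. One limit should be recognised. Section 6.5 already reports 808 patients as actually randomised, so new wording may come too late to change conduct in part or all of the 24-week period. It would still settle the instruction for the extensions and make clear how the week 24 insulin-dose results are to be read.
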